## 6.2 Pre-Study Assessments

Baseline evaluations are to be conducted within 2 weeks prior to start of protocol therapy. CT or PET scan must be done within 4 weeks prior to the start of therapy. Pre-study assessments include:

- Complete medical history and physical examination (including height and weight)
- ECOG Performance Status (see appendix A)
- Charlson Comorbidity Index (see appendix B)
- Laboratory evaluations: CBC with differential; serum chemistries (sodium, potassium, chloride, bicarbonate, magnesium, BUN, serum creatinine, glucose, calcium, liver function tests (LFTs; total bilirubin, alkaline phosphatase, AST, ALT), total protein, albumin, urine or serum pregnancy test in women of childbearing potential)
- Record all concomitant medication(s)
- Tumor evaluation: CT or PET Scan
- Confirmation of EGFR mutation or clinical response to EGFR TKI (see inclusion criteria 3.1.3)
- Toxicity evaluation (for notation of any baseline toxicity) via NCI CTCAE v4.
- Blood sample for Veristat® assay: Draw 3.5 mL SST (gold -top) Vacutainer tube. See section 6.7 for additional details.

## 6.3 Treatment Assessments

### 6.3.1 Post SRS or other Local Ablation

- Symptom directed medical history and physical examination
- ECOG Performance Status (see appendix A)
- Laboratory evaluations: CBC with differential; serum chemistries (sodium, potassium, chloride, bicarbonate, magnesium, BUN, serum creatinine, glucose, calcium, liver function tests (LFTs; total bilirubin, alkaline phosphatase, AST, ALT), total protein, and albumin)
- Toxicity evaluation (for notation of any baseline toxicity) via NCI CTCAE v4.
- Blood sample for Veristat® assay: Draw 3.5 mL SST (gold -top) Vacutainer tube. See section 6.7 for additional details.

### 6.3.2 Every 8 weeks x 3 for a total of 6 months (or until progression, whichever occurs earliest)

- Symptom directed medical history and physical examination
- ECOG Performance Status (see appendix A)
- Laboratory evaluations: CBC with differential; serum chemistries (sodium, potassium, chloride, bicarbonate, magnesium, BUN, serum creatinine, glucose, calcium, liver function tests (LFTs; total bilirubin, alkaline phosphatase, AST, ALT), total protein, and albumin)
- Record all concomitant medication(s) added or changed.

- Tumor evaluation: CT or PET Scan
- Toxicity evaluation (for notation of any baseline toxicity) via NCI CTCAE v4
- Blood sample for Veristat® assay (at first visit post SRS/local ablative therapy only): Draw 3.5 mL SST (gold -top) Vacutainer tube. See section 6.7 for additional details.

### **6.3.3 Subsequent Every 6-12 Weeks until Progression**

For patients who do not progress within the first 6 months on study, following the formal 6 month follow-up post erlotinib initiation at the site, patients will be assessed per standard clinical practice. Typically, this involves serial physical examination, laboratory and imaging evaluations every 6-12 weeks, but this will be done at the discretion of the treating physician. If the patient does not receive his/her clinical care at a participating institution, doctor's notes, imaging reports, and CDs of images will be requested to confirm time of progression, time of death, and toxicity.

### **6.4 Evaluation at Progression**

At the time of progression on erlotinib, the time of documented progression will be recorded. If feasible, obtain blood sample for Veristat® assay: Draw 3.5 mL SST (gold -top) Vacutainer tube. See section 6.7 for additional details. At the time of progression, choice of regimen for next treatment will be requested. If patient is not being treated at an enrolling site, these records may be obtained remotely. Imaging reports and images will be requested to ascertain the nature of and duration of response to the next line of therapy, when possible.

### **6.5 Long-Term Follow-Up**

After progression, follow-up of patients will be limited to collecting response rate and PFS to subsequent therapy when possible, and survival status. If the patient does not receive his/her clinical care at a participating institution, doctor's notes, imaging reports, and CDs of images will be requested to confirm response, time of subsequent progression, and time of death. These data will be collected every 6 months until death, will be recorded on the electronic case report form (eCRF), and may be requested/collected via telephone.

### **6.6 Early Termination Visit**

The following assessments will be performed, if possible, when a subject is withdrawn from study therapy prior to progression:

- Symptom directed medical history and physical examination
- ECOG Performance Status (see appendix A)
- Record all concomitant medications(s) added and/or changed
- Tumor evaluation — CT or MRI Scan and physical examination.
- Toxicity assessment: record any non-serious and serious AEs and assign appropriate toxicity grade (NCI CTCAE, Version 4). Patients who have on ongoing Grade 4 or SAE at the time of discontinuation from treatment will continue to be followed until the event is resolved or deemed irreversible by the investigator.

### 6.7 Correlative Studies Procedures: VeriStrat®

Blood will be obtained and samples blinded at the following intervals:

- At study entry (prior to SRS)
- Subsequent to completion of SRS/local ablative therapy, but prior to reinitiation of erlotinib or that day's dose of erlotinib
- At the first visit following SRS/local ablative therapy
- At the time of progression (if feasible)

The following collection and processing procedures will be followed:

- Biodesix will provide the investigative site with the materials necessary to complete this process.
- Assign a blinded sample number from the Master Worksheet provided by Biodesix. Complete 3 study identification labels with the blinded number.
- Place 1 label on each of the following provided by Biodesix:
  - 3.5 mL SST (gold -top) Vacutainer tube.
  - Serum Collection Card.
  - Study test request form (TRF), upper right corner.
- Collect venous blood into the 3.5 mL SST Vacutainer.
- Gently invert the SST 5 times and allow the tube to clot in an upright position for 30 minutes at room temperature (approximately 70°Fahrenheit or 21°Celcius (C)).
- Spin the SST in a standard clinical centrifuge at a speed of 1000-1300 gravity (g), or equivalent, for 10-15 minutes. Speed should not exceed 1300 g, and time should not exceed 15 minutes or hemolysis may occur.
- Verify that the serum is light yellow in color. Pink or reddish serum indicates sample has hemolyzed and must be redrawn.
- Without disturbing the clot layer, use a transfer pipette to transfer 2 drops (0.1 mL) of serum to each of the 2 circles on the Serum Collection Card.
- Dispose of SST.
- Close cover of Serum Collection Card and follow shipping instructions. Sample must be shipped within 24 hours, and may be stored at room temperature until shipping.

The following shipment procedures will be followed:

- Place the Serum Collection Card into foil bag and seal.
- Place the foil bag and the completed study TRF into the shipping envelope. Save the yellow copy of the study TRF for placement in the subject's study records.
- Complete the required FedEx® air bill fields, and if shipping on a Friday, check the Saturday delivery box. Remove the sender's copy of the air bill for the subject's study records, and place the remainder of the air bill in the pouch in the shipping envelope.
- Arrange for and confirm FedEx pickup of the package the same day as the sample is prepared for shipping.

Any specimens remaining after protocol-directed studies are complete will be destroyed by Biodesix at the completion of the study.

## **6.8 Assessment of Safety**

Any patient who receives treatment on this protocol will be evaluable for toxicity via NCI CTCAE version 4. Further information on this assessment is provided in the time and events table.

## **6.9 Assessment of Efficacy**

Patients who complete SRS (or other local ablation), receive at least 14 doses of erlotinib, and have their disease re-evaluated at 8 weeks will be evaluable for assessment of the primary objective (PFS). Patients who drop out of the study prior to this point will not be evaluable for the primary objective unless they have received at least 14 doses of erlotinib, and have either clearly progressed or died.

If a patient comes off study at any point after 8 weeks without having progressed or died, they will be censored at their last known progression-free date.

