## 2.4 Endpoints

### 2.4.1 Primary

PFS will be measured from the time of initiation of SRS until disease progression or death from any cause

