### **6.9.1 Progression free survival**

Progression free survival will be the primary endpoint of the study. Progression free survival will be measured from the time of initiation of SRS until the time of progression or death. Lesions that progress on initial TKI therapy will be treated with SRS or other locally ablative maneuver. Because of concern for potential antagonism between erlotinib and radiation as well as safety concerns, erlotinib will be held during SRS. This could potentially allow growth of non-treated, erlotinib-sensitive clones during this period, with later disease control on erlotinib. For this reason, non-treated lesions that progress between the pre-treatment and pre-erlotinib reinitiation evaluations will not be counted as progressive disease unless they also progress on the 1st follow-up imaging while on erlotinib. Further, areas treated with SRS are known to sometimes inflame as a consequence of therapy, with no actual disease progression. In clinical practice, radiologist and radiation oncologist assessment of these lesions are predictive of

long-term control. Therefore, clinician judgment will be used for both protocol and treatment decisions in evaluating whether a lesion treated with SRS that appears larger is actually progressive. In all cases, the same judgment must be used for both evaluation of control on study, and clinical decision making.

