#### **8.2 Sample Size and Accrual**

No data exist at this time to define median progression-free survival on chemotherapy, following first-line erlotinib. However, the FDA has approved docetaxel, pemetrexed and erlotinib for second line therapy based on a median

PFS of 1.8-2.9 months, establishing a standard for minimally effective second line therapy.

Study	Regimen	PFS/TTP
Hanna 	Docetaxel Pemetrexed	2.9 2.9 (PFS)
BR.21 	Erlotinib Placebo	2.2 1.8 (PFS)
Shepherd 	Docetaxel Placebo	10.6w 6.7w (TTP)
TAX 320 	Docetaxel Vin or ifos	8.5w 7.9w (TTP)

While a PFS that matched the best previously demonstrated second line results would be sufficient to meet the threshold for further study, several factors are worthy of note in considering how such results could be interpreted and utilized. First, both SRS and erlotinib are substantially less toxic than cytotoxic chemotherapy. Second, this therapy would represent an additional option for EGFR mutant patients—after second progression on erlotinib, patients would still be eligible for treatment with standard chemotherapy. Thus, we hypothesize that the proposed treatment strategy will lead to a median progression free survival of at least 3 months.

A median PFS of 3 months implies that at 3 months, 50% of the population will still be progression free (PF). With 40 patients, the following table shows the precision of the 95% confidence interval that will be constructed for the percentage of patients who are PF at 3 months. If the percentage of patients PF at 3 months is 65% the 95% CI will be (48%-79%).

Number of Pts Progression Free at 3 months	3 month PFS (95% CI)
16/40	40% (25%, 57%)
18/40	45% (29%, 62%)
20/40	50% (34%, 66%)
22/40	55% (38%, 71%)
24/40	60% (43%, 75%)
26/40	65% (48%, 79%)
28/40	70% (53%, 83%)

We expect the percentage of patients who are PF at 3 months to be more than 50%, so with 40 patients, if 65% or 70% of patients are PF at 3 months, the exact 95% binomial confidence interval will be sufficiently narrow and suggest that the median PFS is longer than 3 months. An exact binomial test with a nominal 0.05 one-sided significance level will have 80% power to detect the difference between the null hypothesis of 50% PF at 3 months and the alternative hypothesis of 70% PF at 3 months when the sample size is 40.

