### **8.3 Data Analyses Plans**

Kaplan-Meier curves with appropriate confidence bands will be used to estimate the primary endpoint of median progression free survival. An exact 95% binomial confidence interval for the percentage of patients progression free at 3 months will be also be constructed, and a one-sided test will be done to see if it significantly higher than 50%. While the primary objective is to estimate median PFS, with 40 patients, we may be able to detect a significant improvement over a null hypothesis of only 50% of patients being progression free at 3 months.

Appropriate descriptive statistics including means, standard deviations, medians, and ranges will be provided for continuous data (ex. proteomics), and proportions will be used to summarize categorical data (ex. control and toxicity rates). Standard Kaplan-Meier curves and Cox proportional hazard models will be used to analyze time to event endpoints (including secondary endpoint of OS).

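### Section 6.9 drops patients who progress or die before 14 erlotinib doses from a PFS endpoint that starts at SRS, which inflates the primary estimate; no all-treated PFS analysis is planned

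*Combined protocol and SAP*

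**What the plan says.** - **Endpoint.** Section 2.4.1: "PFS will be measured from the time of initiation of SRS until disease progression or death from any cause". Section 6.9.1 gives the same start and the same events: "Progression free survival will be measured from the time of initiation of SRS until the time of progression or death".
- **Evaluability.** Section 6.9 admits a patient to the PFS analysis after completed ablation, at least 14 doses of erlotinib and the 8-week re-evaluation. For patients who leave sooner, the rule is that they "will not be evaluable for the primary objective unless they have received at least 14 doses of erlotinib, and have either clearly progressed or died".
- **Censoring.** Section 6.9 provides for it only later: "If a patient comes off study at any point after 8 weeks without having progressed or died, they will be censored" at the last date known to be progression free. Event-free patients who leave before 8 weeks are excluded, not censored.
- **Lesion rules.** Section 6.9.1 says that "non-treated lesions that progress between the pre-treatment and pre-erlotinib reinitiation evaluations will not be counted as progressive disease" unless they progress again on the first imaging after erlotinib restarts. It leaves enlargement of SRS-treated lesions to clinical judgement.
- **Analysis.** Section 8.3: "Kaplan-Meier curves with appropriate confidence bands will be used to estimate the primary endpoint of median progression free survival". It adds an exact confidence interval and a one-sided test of the 3-month rate against 50%. Section 8.2: "An exact binomial test with a nominal 0.05 one-sided significance level will have 80% power to detect the difference" between 50% and 70% with 40 patients.
- **Not stated.** Sections 8.2 and 8.3 name no PFS analysis set and give no all-treated PFS analysis, sensitivity analysis or replacement rule. They do not say whether the 40 are treated or evaluable. The only all-treated set, in Section 6.8, is for toxicity.

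**The concern.** Whether a patient enters the analysis depends on what happens after time zero, and failing early is one way to be kept out. Every excluded progression or death before dose 14 would be a failure before 3 months, so it leaves the denominator and never the numerator. For this group the bias has one direction.

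The primary objective is to estimate PFS, so the main harm is an inflated estimate. The margin is narrow: Section 8.2 sets the hypothesis at a median of at least 3 months against 1.8 to 2.9 months for approved second-line treatments. A shift of a few tenths of a month matters to that comparison.

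The rule is also loose at its edge. Section 6.9 does not say whether the 14 doses must follow SRS, while Section 4.3 allows erlotinib to continue through it. The length of the exclusion window therefore depends on how the doses are counted.

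**Working it through.** **Inputs from the documents.** n = 40; null 50% and alternative 70% progression free at 3 months; one-sided 0.05 exact binomial test (Section 8.2); hypothesised median 3 months (Section 8.2); first scheduled follow-up scan at the first of the visits described as "Every 8 weeks x 3 for a total of 6 months" (Section 6.3.2).

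**Assumed.** q, the share of treated patients who progress or die before dose 14 and are excluded. The documents give no value, so q runs over 2.5%, 5%, 10% and 15%, which is 1, 2, 4 and 6 patients in 40 on average.

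**Step 1: the plan's own figure.** With X ~ Binomial(40, 0.5), P(X ≥ 25) = 0.0769 and P(X ≥ 26) = 0.0403, so the test rejects at 26 or more. With rate 0.7, P(X ≥ 26) = 0.807. The stated 80% power is reproduced for 40 analysed patients.

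**Step 2: apparent 3-month rate.** If the true all-treated rate is 0.5 and all excluded patients are early failures, the rate among those left is 0.5/(1 − q). For q = 5%: 0.5/0.95 = 52.6%.

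**Step 3: apparent median.** Beyond the exclusion window, the evaluable curve is S(t)/(1 − q). It reaches one half where S(t) = 0.5(1 − q). For exponential PFS with a true median of 3.0 months, t = 3 × [1 − log2(1 − q)]. For q = 10%: 3 × (1 + 0.152) = 3.46 months.

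**Step 4: type I error, if the 3-month test uses the evaluable set.** Two readings of the 40:
- *40 treated:* the number excluded is Binomial(40, q), the critical value is recomputed for each remaining n, and the rejection probability at 0.5/(1 − q) is averaged.
- *40 evaluable:* P(X ≥ 26) with X ~ Binomial(40, 0.5/(1 − q)).

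| q | Apparent 3-month rate | Apparent median (months) | Type I error, 40 treated | Type I error, 40 evaluable |
|---|---|---|---|---|
| 0 | 50.0% | 3.00 | 4.0% | 4.0% |
| 2.5% | 51.3% | 3.11 | 4.9% | 5.7% |
| 5% | 52.6% | 3.22 | 7.1% | 7.9% |
| 10% | 55.6% | 3.46 | 13.4% | 14.8% |
| 15% | 58.8% | 3.70 | 22.2% | 26.6% |

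**Step 5: single results.**
- 25/40 = 62.5%, p = 0.0769. Drop two early failures: 25/38 = 65.8%, p = 0.0365.
- 24/40 = 60.0%, p = 0.1341. Drop three: 24/37 = 64.9%, p = 0.0494.

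**Step 6: event-free early leavers.** Their exclusion works differently. In a simulation with exponential PFS, median 3 months, and 15% of patients subject to early dropout, removing only event-free leavers before 8 weeks lowered the 3-month Kaplan-Meier estimate from 0.499 to 0.489. Removing all events before week 3 as well gave 0.581. The net effect was still upward there, but that case assumes that every early event is recognised.

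**Separate case, not to be added to the above.** If the 40 are treated patients and loss is unrelated to outcome, average power at 70% is about 77%, 76% and 73% for 5%, 10% and 15% lost, against 80.7%. If the 40 are evaluable, this does not arise.

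**The case against.** The strongest reply is that few patients will fail so early. Eligibility requires ECOG 0 or 1, adequate organ function and at most five sites that can be ablated. The post-SRS visit has no tumour evaluation and the first scheduled scan is at 8 weeks, so mainly deaths and clinically evident progression would be seen before dose 14. Section 6.9.1 already discounts some growth of untreated lesions, so not every early enlargement is an event. If doses taken during SRS count, the window shortens. At q = 2.5% the median moves 0.1 month, against a sampling standard deviation of about 0.7 month for a median from 40 uncensored exponential times, and type I error stays under 5% if the 40 are treated. All of this stands as an argument about size. It does not make the exclusion neutral: sampling error has no preferred direction, and this bias does.

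Second, Section 6.9 limits evaluability for the primary objective, and Section 8.3 presents the 3-month test as secondary to estimating the median, with no go/no-go rule attached. The documents never say that the test uses the evaluable set. That is correct, and the type I figures are conditional on it. The bias in the Kaplan-Meier estimate does not depend on it.

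Third, a treated-and-assessed set can be a legitimate choice for an objective about ablation followed by erlotinib, and overall survival has no evaluability limit, so early deaths are visible there. But a set chosen by later treatment does not fit a clock that starts at SRS, and overall survival does not repair the PFS estimate.

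**Conclusion.** The concern holds. As written, Section 6.9 removes early progressions and deaths that Sections 2.4.1 and 6.9.1 count as events, and no all-treated PFS analysis shows the effect. The bias from excluding these patients is upward. For the rule as a whole, the exclusion of event-free early leavers adds an effect of uncertain direction.

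The size cannot be fixed from the documents. The tabulated shifts rest on the assumed q, and the medians also on exponential PFS. With scans 8 weeks apart, they indicate scale and are not forecasts. The low end may be the more likely. Under the 40-treated reading, the test exceeds its nominal 5% once more than about 1 treated patient in 40 is an excluded early failure; under the 40-evaluable reading it already does so at that level. The stated power is correct for 40 analysed patients. Because the primary estimate itself is affected and the remedy is nearly free, this should be corrected before analysis.

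**What to change.** In Sections 6.9, 8.2 and 8.3:

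1. Define the primary PFS set as all patients who start SRS or other local ablation, with time zero at that start.
2. Count death from any cause and progression from that date, keeping the Section 6.9.1 rules on untreated and SRS-treated lesions.
3. In the Kaplan-Meier analysis, censor event-free withdrawals at the last date known to be progression free, whether before or after 8 weeks.
4. State in advance which set the 3-month binomial analysis uses and how it treats unknown status at 3 months.
5. Keep the 14-dose, 8-week evaluable set as a sensitivity analysis, and say whether its 14 doses are counted from after SRS.
6. State that the 40 in Section 8.2 refers to the all-treated set.

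The cost is wording: no new visits or data, since the plan already records progression and survival. Reported PFS may be slightly less favourable. Event-free patients who leave without any follow-up tumour evaluation would be censored near time zero and add little; Section 6.6 asks for a tumour evaluation at early termination where possible, which limits this. If few patients fail early, counting them changes little.

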**Key to Time and Events Table**

 Unless otherwise noted, perform within 2 weeks prior to initiation of SRS or local ablative therapy. CT or PET within 4 weeks prior to the start of therapy

 Post SRS or local ablative therapy, pre-erlotinib unless patient enrolled in trial on erlotinib and continuing it through SRS, see section 4.3 (NOTE: this visit can occur on the last day of radiation)

 The initial 3 visits post erlotinib initiation will be performed at the enrolling site, and can take place every 8 weeks +/- 1 week; however, the tumor measurements at these visits should take place within 1 week (7 days) prior to the study visit. If patient progresses prior to the end of 6 months, then they will enter long-term follow-up (see section 6.5).

 For patients living a distance prohibitive for further travel to the enrolling site, visits after the initial 6 months on erlotinib (or after progression) for clinical care may be performed remotely by the patient's primary oncologist. In this case, records will be requested, specifically including doctors' notes, imaging reports, and CDs of imaging.

 This visit will be scheduled when a subject is withdrawn from study therapy prior to progression

 At the time of progression, choice of regimen for next treatment will be requested. If patient is not being treated at an enrolling site, these records may be obtained remotely. Imaging reports and images will be requested to ascertain the nature of and duration of response to the next line of therapy, when possible.

 Complete medical history at baseline, thereafter, symptom directed history

 Serum or urine pregnancy test for women of child bearing potential

 Serum chemistries include sodium, potassium, chloride, bicarbonate, magnesium, BUN, serum creatinine, glucose, calcium, total protein and albumin; liver function tests include total bilirubin, alkaline phosphatase, AST, and ALT)

 CT or PET scan-use consistent imaging throughout study; NOTE: the X at progression is there to indicate that progression was diagnosed via a tumor evaluation

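### The exact binomial interval and test at 3 months have no rule for patients censored before 3 months, although section 6.9 allows such censoring

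*Combined protocol and SAP*

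**What the plan says.** All references are to the combined protocol and SAP.

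- **Censoring (section 6.9).** Of patients who leave at any time after 8 weeks without progression or death, the plan says that "they will be censored at their last known progression-free date". For those who leave before the 8-week evaluation: "Patients who drop out of the study prior to this point will not be evaluable for the primary objective", unless they have had at least 14 erlotinib doses and have progressed or died.
- **Primary estimate (section 8.3).** "Kaplan-Meier curves with appropriate confidence bands will be used to estimate the primary endpoint of median progression free survival".
- **3-month analysis (section 8.3).** "An exact 95% binomial confidence interval for the percentage of patients progression free at 3 months will be also be constructed", followed by a one-sided test of whether that percentage exceeds 50%.
- **Power (section 8.2).** "An exact binomial test with a nominal 0.05 one-sided significance level will have 80% power" to distinguish the "null hypothesis of 50% PF at 3 months and the alternative hypothesis of 70% PF at 3 months when the sample size is 40". Every row of the precision table has denominator 40. No dropout rate or allowance is stated.
- **Timing.** PFS runs from the start of SRS (section 2.4.1). Visits are every 8 weeks, plus or minus 1 week, after erlotinib initiation, and "the tumor measurements at these visits should take place within 1 week (7 days) prior to the study visit" (key to the Time and Events table).
- **Leaving early (section 6.6).** A tumor evaluation is planned on withdrawal before progression, but only where it can be done.

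**The concern.** A binomial proportion needs a yes or no for every patient in its denominator. Section 6.9 creates patients who have neither: they were progression free when last seen, and that date precedes 3 months. Kaplan-Meier uses them up to that date; the exact binomial cannot. Sections 8.2 and 8.3 do not say whether such a patient is dropped, counted as a failure or counted as progression free.

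At stake are the 3-month confidence interval and the only hypothesis test that the plan states. If the handling is chosen once the data are in, the analyst can pick between a significant and a non-significant result. Two of the three choices also cost power that the design cannot spare.

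**Working it through.** **1. The plan's own figure.** With n = 40, null rate 0.50 and one-sided 0.05, the smallest cut-off r with P(X ≥ r | 40, 0.5) ≤ 0.05 is 26. It gives an exact type I error of 0.0403 and power P(X ≥ 26 | 40, 0.7) = 0.807. The stated 80% reproduces, and so do all seven intervals in the precision table. A cut-off of 25 would give a type I error of 0.077, so there is no slack.

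**2. Where the scans fall.** Assume SRS takes 1 to 15 days (up to ten daily lung fractions, section 4.2.2f; the documents set no limit on the total) and that erlotinib starts 0 to 3 days later (section 4.3). Days are counted from SRS start:
- Scan 1, earliest: 1 + 0 + 56 − 7 − 7 = 43. Latest: 15 + 3 + 56 + 7 = 81.
- Scan 2, earliest: 1 + 0 + 112 − 7 − 7 = 99. Latest: 15 + 3 + 112 + 7 = 137.

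Three months is about day 91, between the two ranges. If two early visit windows accumulate, scan 2 could come at about week 13, still at or just after 3 months. A patient who leaves between the scans, with no progression-free assessment on or after 3 months, is censored before 3 months. Section 6.5 describes follow-up only after progression, so no later scan is specified for this patient.

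**3. The choice can decide the test.** Take 24 known progression free, 12 failures and 4 censored early:

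| Handling of the 4 | Result | One-sided p | Exact 95% CI |
|---|---|---|---|
| Dropped | 24/36 | 0.033 | 49% to 81% |
| Failures | 24/40 | 0.134 | 43% to 75% |
| Progression free | 28/40 | 0.008 | 53% to 83% |

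**4. Power over a range of leaving rates.** The documents give no rate, so d, the fraction of patients progression free at scan 1 who leave before scan 2, is assumed. PFS is taken as exponential with a 3-month rate of 70%, and leaving as non-informative with censoring at 2.3 months.
- Progression free at 2.3 months: 0.7^(2.3/3) = 0.761.
- Expected leavers: 40 × 0.761 × d. This is 0.9, 3.0 or 6.1 patients for d = 3%, 10% or 20%.
- Rate the binomial sees, for d = 10%: as failures, 0.7 × 0.9 = 0.630; dropped, 0.630 / (1 − 0.0761) = 0.682; as progression free, 0.630 + 0.0761 = 0.706.

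Dropping therefore lowers the observed rate as well as n, because every leaver was progression free at scan 1. Simulated power (6,000 replicates, good to about one percentage point; cut-off re-derived when n shrinks):

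| d | Dropped | Failures | Progression free | Kaplan-Meier |
|---|---|---|---|---|
| 3% | 76% | 72% | 82% | 81% |
| 10% | 68% | 46% | 83% | 79% |
| 20% | 54% | 16% | 86% | 77% |

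**5. The Kaplan-Meier test without early censoring.** On the complementary log-log scale, z = [ln(−ln 0.5) − ln(−ln S)] / se, where se = √[(1 − S)/(40 S)] / |ln S|. For 26/40, z = 0.476/0.269 = 1.77, above 1.645. For 25/40, z = 0.389/0.261 = 1.49, below it. The cut-off is again 26, so the two tests agree.

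**6. Type I error.** At a true rate of 50% with non-informative leaving of 10%, the Kaplan-Meier test has simulated size of about 4%. If instead up to 3 leavers are patients who would have progressed before 3 months, size is about 16% for Kaplan-Meier, 16% if they are counted as progression free, 10% if dropped and 4% if counted as failures.

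**The case against.** The strongest reply is that the primary objective is to estimate median PFS, that Kaplan-Meier already handles this censoring, and that the 3-month test is supplementary with no go/no-go rule attached. That is correct and limits the weight of the point. It does not supply the missing rule.

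Three stronger readings are tempting, and the documents do not support them.

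- **Every patient censored under section 6.9 lacks a 3-month status.** The rule covers leaving at any time after 8 weeks. Those who leave after scan 2 are normally known to be progression free at 3 months. A leaver between the scans may have an exit scan after day 91, and section 6.9 does not tie the last progression-free date to a scheduled scan. The scan ranges also depend on SRS duration: up to five sites may be treated, and if SRS took four weeks scan 1 could fall at 28 + 3 + 56 + 7 = day 94, after 3 months.
- **Power is always lost.** Counting leavers as progression free raises it, at the risk of a larger type I error. If exactly 3 patients are removed at random, the cut-off becomes 24/37 and power stays at 80.7%, because exact cut-offs move in steps. That calculation keeps a 70% rate among those who remain, which does not hold when the leavers are selected for being progression free at scan 1.
- **Kaplan-Meier keeps the error rate whoever leaves.** It does so only under non-informative leaving. Setting its 4% from that case against an inflated figure from informative leaving would mix two scenarios; under informative leaving it does about as badly as counting leavers as progression free.

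It is also fair that leaving rates of 10% to 20% between two scans are illustrative. At 3%, under one patient on average, the loss is modest.

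**Conclusion.** The point stands in limited form. The censoring rule in section 6.9 and the exact binomial in sections 8.2 and 8.3 do not fit together for patients whose last progression-free date precedes 3 months, and the plan does not say how to treat them. Four such patients are enough to move p between 0.008 and 0.134. Under non-informative leaving of 3% to 20%, power at 70% falls to between 76% and 54% if they are dropped and between 72% and 16% if they are counted as failures; Kaplan-Meier holds 81% to 77%.

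These sizes rest on an assumed leaving rate, exponential PFS, SRS lasting no more than about two weeks and no exit scan after 3 months. The median PFS estimate is not affected. The change should be made, but the point does not undermine the trial's primary estimate.

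**What to change.** In section 8.3, take the 3-month progression-free rate, its 95% confidence interval (complementary log-log) and the one-sided 0.05 test against 50% from the Kaplan-Meier curve already planned. Keep the exact binomial as a named sensitivity analysis in which any patient without a known 3-month status counts as not progression free. Report the two side by side, with the number of such patients. The sensitivity analysis is needed because Kaplan-Meier gives no protection if leavers are patients about to progress.

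The cost is a few sentences and a few lines of code, with no extra patients or visits. The downside is that the main 3-month test becomes large-sample rather than exact when there is early censoring. With none, it reaches the same decision as the exact test at n = 40, so the stated 80% power carries over.
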